## 4. COLLECTION, RECORDING, AND REPORTING OF SAFETY INFORMATION AND PRODUCT COMPLAINTS

In the situation that an adverse event, product complaint and/or other safety finding is identified/reported, these will be reported to Amgen Safety consistent with standard practices.

#### 4.1 Definition of Reportable Events

#### 4.1.1 Adverse Events

An adverse event is any untoward medical occurrence in a subject/patient administered a pharmaceutical product(s) irrespective of a causal relationship with this treatment.

An adverse event can therefore be any unfavorable and unintended sign (including an abnormal laboratory finding, for example), symptom, or disease temporally associated with the use of a product(s), whether or not considered related to the product(s). The definition of an adverse event includes:

- Worsening of a pre-existing condition or underlying disease
- Events associated with the discontinuation of the use of a product(s), (eg, appearance of new symptoms)

It is Naxion's responsibility to evaluate whether an adverse event is related to an Amgen product prior to reporting the adverse event to Amgen.

# 4.1.2 Serious Adverse Events A serious adverse event is any adverse event as defined above that meets at least one of the following serious criteria:

- is fatal
- is life threatening (places the patient at immediate risk of death)
- requires in-patient hospitalization or prolongation of existing hospitalization
- results in persistent or significant disability/incapacity
- is a congenital anomaly/birth defect
- is an "other medically important serious event" that does not meet any of the above criteria

Abbreviated Protocol: 20210065

Date: 22 March 2021 Page 8 of 37

A hospitalization meeting the regulatory definition for "serious" is any in-patient hospital admission that includes a minimum of an overnight stay in a healthcare facility.

"Other medically important serious events" refer to important medical events that may not be immediately life-threatening or result in death or hospitalization but may jeopardize the patient or may require intervention to prevent one of the other outcomes listed in the definition above. Examples of such events could include allergic bronchospasm, convulsions, and blood dyscrasias, drug-induced liver injury, events that necessitate an emergency room visit, outpatient surgery, or other events that require other urgent intervention.

### 4.1.3 Other Safety Findings

Other Safety Findings (regardless of association with an adverse) include:

- Medication errors, overdose/underdose, whether accidental or intentional, misuse, addiction, or abuse, involving an Amgen product,
- Use of an Amgen product while pregnant and/or breast feeding ,
- Transmission of infectious agents,
- Reports of uses outside the terms for authorized use of the product including off-label use.
- Accidental or Occupational exposure,
- Any lack or loss of intended effect of the product(s).

### 4.1.4 Product Complaints

Product Complaints include any written, electronic or oral communication that alleges deficiencies related to the identity, quality, durability, reliability, safety, effectiveness, or performance of a drug, combination product, or device after it is released for distribution to market or clinic. This includes any drug(s), device(s) or combination products provisioned and/or repackaged /modified by Amgen. Drug(s) or device(s) or combination product(s) includes investigational product. Amgen will collect product complaints for BLINCYTO.

## 4.2 Safety Collection, Recording and Submission to Amgen Requirements

This study is collecting information from HCPs at a point in time (survey). All reportable events (adverse events, product complaints, and other safety findings) reported by the HCP or interviewer that occur in patients treated with BLINCYTO will be collected from HCP enrollment to final study contact during the pretest and main survey. The Vendor (Naxion) is responsible for ensuring that all reportable events (adverse events, product

Abbreviated Protocol: 20210065

Date: 22 March 2021 Page 9 of 37

complaints and other safety findings) they become aware of during the study period (including the pretest and main survey) are recorded in the appropriate study documentation. Additionally, these reportable events must be reported by the HCP or interviewer that occur in patients treated with BLINCYTO after study enrollment through the final study contact and are recorded in the HCP's study documentation. If further safety related data is needed to fulfill any regulatory reporting requirements for a reportable event, then additional information may need to be collected from the subject's/patient's records and provided by the nurse or pharmacist..

All reportable events must be submitted as individual case safety reports to Amgen via the applicable Amgen Safety Reporting Form (paper or electronic form) within 1 business day of awareness (Table 1). Non-serious Adverse Events (AEs) must be reported in an expeditious manner, not to exceed 15 calendars days of Vendor (Naxion) awareness.

Reportable events that are suspected to be related to any medicinal product where there is no exposure to Blincyto must be reported to the local authority in line with the local country requirements.

See Appendix C. for the Amgen Safety Reporting Form, Appendix D. for Additional Safety Reporting Information regarding the adverse event grading scale used in this study, and Appendix E. for sample Pregnancy and Lactation Notification Forms.

The HCP may be asked to provide additional information for any event submitted, which may include a discharge summary or extracts from the medical record. Information provided about the event must be consistent with medical records and information recorded in the study documentation where safety data may also be recorded.

Table 1 Types of Safety Data to be Collected and Reported in Primary Data Collection Studies Collecting all Reportable Events

Reportable Events/Event Type	* Reporting Timeframe	
Serious Adverse Events (related and non-related)	Within 1 business day from when < <investigator vendor="">> first</investigator>	

 
Product Complaints (serious and non- serious)
 
	becomes aware of the event	

 
Other Safety Findings (serious and non-serious)
 
		
Pregnancy and/or Lactation Exposure		

Abbreviated Protocol: 20210065

Date: 22 March 2021 Page 10 of 37

Non-serious Adverse Events (related and non-related)
 Within 15 calendar days from when Investigator/Vendor first becomes aware of the event

#### **Female Subjects Who Become Pregnant**

The Vendor (Naxion) will collect pregnancy information on any female subject/patient who becomes pregnant following exposure to BLINCYTO through 48 hours.

Information will be recorded on the Pregnancy Notification Form (see Appendix E). The form must be submitted to Amgen Safety within 1 business day of learning of when the Vendor first becomes aware the subject's pregnancy. (Note: Vendor is not required to provide any information on the Pregnancy Notification Form that violates the country or regions local privacy laws).

After receipt of the Pregnancy Notification Form, Amgen Safety will provide Investigator with a consent form and questionnaire to collect additional information. After obtaining the female subject's signed consent for release of pregnancy and infant health information, the Vendor will collect pregnancy and infant health information and complete the pregnancy questionnaire for any female subject who becomes pregnant following exposure to BLINCYTO through 48 hours of the BLINCYTO. This information will be forwarded to Amgen Safety. Generally, infant follow-up will be conducted up to 12 months after the birth of the child (if applicable). Any termination of pregnancy will be reported to Amgen Safety, regardless of fetal status (presence or absence of anomalies) or indication for procedure. While pregnancy itself is not considered to be an adverse event or serious adverse event, any pregnancy complication or report of a congenital anomaly or developmental delay, fetal death, or suspected adverse reactions in the neonate will be reported as an adverse event or serious adverse event. Note that an elective termination with no information on a fetal congenital malformation or maternal complication is generally not considered an adverse event, but still must be reported to Amgen as a pregnancy exposure case.

If the outcome of the pregnancy meets a criterion for immediate classification as a serious adverse event (eg, female subject experiences a spontaneous abortion, stillbirth, or neonatal death or there is a fetal or neonatal congenital anomaly) the Vendor will report the event as a serious adverse event.

\* Please note, more stringent reporting timelines may apply per local requirements

Collection of Pregnancy and Lactation Information

Date: 22 March 2021 Page 11 of 37

## Male Subjects with Partners who Become Pregnant [or Were Pregnant at the Time of Enrollment]

In the event a male subject fathers a child following exposure to BLINCYTO, and for an additional 48 hours after discontinuing BLINCYTO, the information will be recorded on the Pregnancy Notification Form. The Form (see Appendix E) must be submitted to Amgen Safety within 1 business day of when the Vendor first becomes aware of the pregnancy. (Note: The Vendor is not required to provide any information on the Pregnancy Notification Form that violates the country or regions local privacy laws).

After receipt of the Pregnancy Notification Form, Amgen Safety will provide Investigator with a consent form and questionnaire to collect additional information. The Vendor will attempt to obtain a signed consent for release of pregnancy and infant health information directly from the pregnant female partner to obtain additional pregnancy information.

After obtaining the female partner's signed consent for release of pregnancy and infant health information, the Vendor will collect pregnancy outcome and infant health information on the pregnant partner and her baby and complete the pregnancy questionnaires. This information will be forwarded to Amgen Safety.

Generally, infant follow-up will be conducted up to 12 months after the birth of the child (if applicable). Any termination of the pregnancy will be reported to Amgen Global Patient Safety regardless of fetal status (presence or absence of anomalies) or indication for procedure.

#### **Collection of Lactation Information**

Vendor will collect lactation information on any female subject who breastfeeds while taking BLINCYTO through 48 hours.

Information will be recorded on the Lactation Notification Form (see Appendix E) and submitted to Amgen Safety within 1 business day of when the Vendor first becomes aware of the lactation exposure. With the female subjects signed consent for release of mother and infant health information, the Vendor will collect mother and infant health information and complete the lactation questionnaire on any female subject who breastfeeds while taking BLINCYTO through 48 hours after discontinuing BLINCYTO.

## 4.2.1 Safety Reporting Requirement to Regulatory Bodies

Amgen will report safety data as required to regulatory authorities,
Investigators/institutions, IRBs/IECs or other relevant ethical review board(s) in
accordance with Pharmacovigilance guidelines and in compliance with local regulations.

**Abbreviated Protocol: 20210065** 

Date: 22 March 2021 Page 12 of 37

The Investigator is to notify the appropriate IRB/IEC or other relevant ethical review board of reportable events in accordance with local procedures and statutes.

Abbreviated Protocol: 20210065

Date: 22 March 2021 Page 13 of 37

#### 5. SUBJECT CONFIDENTIALITY

This study will comply with all applicable laws regarding subject privacy. No direct subject contact or collection of additional subject data will occur. Study results will be in tabular form and aggregate analyses that omits subject identification. Any reports will not include subject identifiers.

#### 6. PUBLICATION INTENT

There is no intent to publish the results of these analyses.

## 7. COMPENSATION

Healthcare professionals will receive payment for their participation in the surveys.

This compensation will be based on a Fair Market Value (FMV) assessment (eg, time and effort).

**Table 2: Survey Respondent Compensation** 

Healthcare provider	Compensation for online survey (\$)
Pharmacist	\$65
Registered nurse	\$65

Abbreviated Protocol: 20210065

Date: 22 March 2021 Page 14 of 37

## Appendix A. Questionnaire

## Screening questions:

Have you personally prepared, dispensed, and/or administered BLINCYTO
therapy to patients outside of the clinical trial setting in the last 12 months?
(Select all that apply)

a. I have personally prepared BLINCYTO therapy outside the clinical trial setting	0	
b. I have personally dispensed BLINCYTO therapy outside the clinical trial setting	0	
c. I have personally administered BLINCYTO therapy outside the clinical trial setting	0	
d. None of the above	0	TERMINATE

## PROGRAMMING:

#### 1) Ask all respondents

1a. Approximately how many BLINCYTO infusions have you prepared, dispensed, or administered outside of the clinical trial setting in the last 12 months?

	Number of infusions	
-		

#### PROGRAMMING:

#### 1) Ask all respondents

1b. How many patients have you prescribed, dispensed, prepared, and/or administered BLINCYTO therapy to outside of the clinical trial setting in the past 12 months?

[#]	patients	who	have	received	BLINC	YTO
-----	----------	-----	------	----------	--------------	-----

#### PROGRAMMING:

- 1) Ask all respondents
- 2) Terminate if 0

Abbreviated Protocol: 20210065

Date: 22 March 2021 Page 15 of 37

2. In what country is your workplace located? If you workplace in more than one country, please select the primary country in which you work.

(Select one answer)

[Drop down list of standard responses]

#### PROGRAMMING:

1) Ask all respondents

- 2) If workplace is located in the U.S. and territories, proceed to Question 3; others TERMINATE
- 3. In what state is your workplace located? If you work in more than one state, please select the state where you consider your primary workplace to be located.

(Select one answer)

[Drop down list of states]

#### PROGRAMMING:

- 1) Ask all respondents
- 2) VT and ME responders: give option to continue but decline compensation
- 4. Are you or any member of your immediate family (household) currently, or have been previously, employed in any capacity (eg, clinical investigator, consultant, researcher, etc.) by Amgen, Naxion, or the FDA?

(Select one answer)

a. Yes	TERMINATE
b. No	

## **PROGRAMMING:**

1) Ask all respondents

Abbreviated Protocol: 20210065

Date: 22 March 2021 Page 16 of 37

5. What type of healthcare provider are you?

(Select one answer)

a. Doctor (MD, DO)	0	TERMINATE
b. Physician Assistant/Nurse Practitioner	0	TERMINATE
c. Registered Nurse	0	
d. Hospital-Based Clinical Pharmacist	0	
e. Home Healthcare Pharmacist	0	
f. Director of Pharmacy	0	
g. Other (please specify:)	0	TERMINATE

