#### 2. OBJECTIVES

The broad objective of this study is to determine the level of awareness of the risks and safety associated with BLINCYTO therapy and certain aspects of the BLINCYTO REMS Program among pharmacists and nurses who have used BLINCYTO for patients in the treatment of relapsed or refractory B-cell precursor acute lymphoblastic leukemia (ALL). The specific objective is to:

 Evaluate the awareness and understanding of the preparation and administration errors associated with BLINCYTO use among pharmacists who have prepared BLINCYTO, and nurses who have administered BLINCYTO.

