#### **Study Population**

Inclusion criteria include HCPs, defined as nurses (RNs, BSNs), and hospital and/or home healthcare pharmacists who have dispensed, prepared and/or administered BLINCYTO therapy to patients outside of the clinical trial setting in the past 12 months. HCPs or their immediate family members (eg, spouse, children, and/or parent) who are or were employed by Amgen, Naxion, or the FDA will be excluded from participation. HCPs who have been part of previous assessments (at 18 months, 3 years, and 5 years after the launch of BLINCYTO) will also be eligible to participate.

A list of HCPs targeted by the REMS Program will be matched to the survey vendor's Panels and/or other target sources to determine a list of respondents. All HCPs that are identified via these sources will be invited to participate in this survey.

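### Screener Question 5 is narrower than the inclusion criterion, so an eligible hospital pharmacist who prepared BLINCYTO but does not identify as clinical can be terminated

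*Protocol*

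**What the plan says.** Protocol, Objectives: the specific objective concerns understanding of preparation and administration errors among "pharmacists who have prepared BLINCYTO, and nurses who have administered BLINCYTO".

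Protocol, Study Population: besides nurses, the eligible group is "hospital and/or home healthcare pharmacists who have dispensed, prepared and/or administered BLINCYTO therapy to patients outside of the clinical trial setting" within the past 12 months. No job title within the hospital is required.

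Protocol, Appendix A, screening Question 5: the respondent picks one provider type. Three options lead to the pharmacist questions: "d. Hospital-Based Clinical Pharmacist", "e. Home Healthcare Pharmacist" and "f. Director of Pharmacy". The residual option, "g. Other (please specify", is marked for termination. The programming note after Question 5 sends only those three options to the pharmacist items.

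Protocol, Survey Methodology: respondents whom the screener finds ineligible leave the survey, and participants cannot go back to a question.

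**The concern.** The inclusion criterion and the screener should define the same population, and here they do not. The criterion turns on workplace type and recent use of the drug. Question 5 adds the word clinical to the only general hospital option.

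A hospital pharmacist who prepares infusions, and who would describe the job as staff or compounding, is eligible under the criterion and passes the first screening question by reporting personal preparation. That person can still be turned away at Question 5 over a job label.

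This touches the people the objective names, pharmacists who have prepared the drug. The share of pharmacists judged to have knowledge will be compared with a threshold of 80% for that provider type, so it matters who is able to enter the pharmacist sample.

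**Working it through.** **1. Trace eligible pharmacists through the screener.** All rows assume use of the drug in the past 12 months outside trials, so all meet Study Population and pass Question 1.

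| Respondent | Question 5 answer | Outcome |
|---|---|---|
| Hospital clinical pharmacist | d | continues |
| Home healthcare pharmacist | e | continues |
| Director of pharmacy | f | continues |
| Hospital staff or compounding pharmacist who treats d as the nearest fit | d | continues |
| Hospital staff or compounding pharmacist who does not identify as clinical and answers literally | g | terminated |

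The last row is the gap: an eligible person with no qualifying option. The two last rows differ only in how the respondent reads one word.

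**2. Look for text that closes the gap.** Nothing in Question 5 says that option d covers all hospital pharmacists. No step is described in which the free text under option g is read before the survey ends. Elsewhere the protocol uses the wider term: Survey Pre-testing speaks of hospital-based pharmacists, and Background and Rationale and Question 25 refer to a REMS letter for hospital and home healthcare pharmacists. Only Question 5 adds the qualifier, and no reason is given.

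**3. Check whether the stated precision is affected.** Inputs from Sample Size: n = 100 pharmacists, 95% confidence, and the 20% column of the precision table, which by symmetry also applies at 80%. Half-width = 1.96 × √(p(1 − p)/n) = 1.96 × √(0.20 × 0.80/100) = 0.0784, which matches the tabulated 0.078. The formula depends only on n and p, so with 100 pharmacists still recruited the figure stands. The problem is who is covered, not precision.

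**4. See whether the effect on the estimate can be sized.** Let e be the share of eligible pharmacists who are terminated, and d the knowledge proportion among those retained minus that among those terminated. The estimate is then off by e × d. The protocol gives no distribution of pharmacist roles, no share who would choose option g, and no knowledge figures by role. Neither e nor the sign or size of d is available, so no number is put on the effect.

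**5. Ask whether the pre-test would catch it.** About 5 hospital-based pharmacists are to be pre-tested. If a share q of such pharmacists would choose option g, the chance that none of 5 does so is (1 − q)^5. With q assumed, since the protocol gives no value: q = 10% gives 0.9^5 = 0.59, and q = 20% gives 0.8^5 = 0.33. On those assumptions, missing the gap and finding it are both realistic outcomes.

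**The case against.** The strongest reply has three parts.

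First, the protocol has a step meant for this kind of problem. The pre-test is to confirm that closed-ended lists omit no reasonable option, and its findings shape the final instrument, so Appendix A may not be what is fielded. This stands in part. The pre-test could find the gap, but it is small, and a list ending in a residual option already looks complete. As written, the protocol leaves the mismatch unresolved.

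Second, exclusion is inferred. Option d is the only general hospital option, and a preparing pharmacist could reasonably choose it. This stands as a limit on the claim: such pharmacists can be terminated, and nothing shows how many would be. It does not make the screener agree with the criterion.

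Third, a reader might infer more than the text bears. One inference is that the sample shifts toward managers because directors are admitted while preparers are lost. Question 1 ends the survey for anyone who has not personally prepared, dispensed or administered the drug, so an admitted director has also handled it, and no shift is shown. Another is that staff and compounding pharmacists would be wholly absent. Those who choose option d remain, so that does not follow either. Nor does the point extend to pharmacists at infusion centres outside hospitals, who are not in the inclusion criterion unless they work in home healthcare, or to registered nurses, who have their own option.

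**Conclusion.** The point holds as a coverage mismatch. Question 5 is narrower than the Study Population criterion, and it can end the survey for a hospital pharmacist whom the criterion admits and the objective names. This follows from comparing the two sections and needs no numerical assumption. For anyone actually to be lost, at least one eligible hospital pharmacist must not identify as clinical and must answer literally; how often that happens is not known.

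A reader might go on to infer that the pharmacist result will be biased by some number of points, or pushed to one side of the 80% threshold. The documents do not support that: the size and the direction of any effect are both undetermined, and the stated precision is unchanged. This is a modest defect, worth correcting because the correction is nearly free before fielding, whereas respondents already terminated cannot be recovered in the analysis.

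**What to change.** Two changes to Question 5 before fielding:

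- Reword option d to: Hospital-based pharmacist (any role, e.g. clinical, staff or compounding). This brings it into line with Study Population.
- Under option g, do not terminate when the specified role is a hospital or home healthcare pharmacist; route that respondent to the pharmacist questions. Other answers under g still terminate. Online, a single yes/no follow-up could do this without anyone having to read free text in real time.

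The routing note after Question 5 then needs a matching edit. The cost is one answer label and one routing rule in the online and telephone programs. No extra respondents are needed, and the sample size and analysis do not change.

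If the sponsor does intend to restrict the hospital group to clinical pharmacists and directors, Study Population should say so instead, with the reason.
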